Morphological, Functional and Tissue Characterization of Silent Myocardial Involvement in Patients with Primary Biliary Cholangitis

Early Identification of Myocardial Impairment in PBC (EARLY-MYO-PBC)

Protocol Number	201709P-01
Version (Date)	2.0.0 (September 25, 2017)
NCT No.	NCT03545672

STUDY PROTOCOL SYNOPSIS

Title	Morphological, Functional and Tissue Characterization of Silent Myocardial
	Involvement in Patients with Primary Biliary Cholangitis
Sponsor	Investigator-Initiated Trial (IIT)
Primary Objectives	 The incidence of cardiac involvement (LGE and T2-STIR positive) Late gadolinium enhancement (LGE) indicates myocardium viability in patients which can be recognized by regional high signal area in cardiac image. Meanwhile, T2-STIR positive indicate the myocardium edema. The outcome assessments base on the presence of myocardium late gadolinium enhancement and T2-stir positive in all participants Quantitative assessment in cardiac injury T1 mapping–derived extracellular volumes (ECV) were used to detect changes in the myocardium interstitial matrix. ECV was calculated according to the ECV formula including T1 mapping value.
Study Design	 EARLY-MYO-PBC study was a prospective, three-center, multi-modality cardiac imaging study (Trial Registration: NCT03545672) designed to early identify silent myocardial impairment in PBC patients. We hypothesized that myocardial injuries could occur at the early-stage of PBC without presenting any reported cardiac clinical manifestation. Participants undergoing cardiovascular magnetic resonance (CMR) were enrolled. Demographic, serological, and cardiac imaging data were prospectively collected. All participants were free of cardiac discomfort or a prior history of heart disease and had normal electrocardiographic results. (1) CMR Protocol All images were acquired and then processed in a core lab 1. The LV volumetric and systolic assessment was performed with cine imaging by whole-heart coverage using a balanced, steady-state, free precession sequence in combination with parallel imaging and retrospective gating during a gentle, expiratory breath hold. T2 maps were acquired in several contiguous short axis slices, using a multi-echo GraSE black-blood sequence. An electrocardiogram-triggered, STIR T2-weighted multi-slice spin-echo sequence also was performed to determine edema and the T2 ratio. T2*-mapping is used for detecting iron deposition. Native and post-contrast myocardial T1 mapping were used to determine the ECV. A MOLLI R5.1 sequence was used for T1 mapping, and a "5-3-3" scheme (in seconds) was chosen. The scheme was performed on a 3 mid-diastolic LV short-axis slice (basal, mid-ventricle, and apex) before and 15 min after a bolus intravenous injection of 0.15 mmol/kg gadobutrol (Bayer Healthcare, Berlin, Germany). Segmented LGE images with at least three matching slices and native T1 images were also acquired. Visual assessment of LGE positive (LGE+) was recorded. The detailed methods and acquisition parameters can be found in publication 2: Arthritis & Rheumatolegy web site at the state of the formal mapping.

	(2) Image Analysis
	All contours were manually examined, adjusted if necessary and assessed.
	Myocardial deformation was voxel-tracked to acquire LV global circumferential
	strain (GCS), global longitudinal strain (GLS) and global radial strain (GRS). The
	LGE was examined for the presence of regional fibrosis. T1, ECV images were
	examined for extent of extracellular volume. Reported T1 values were derived
	with the operator blinded to the LGE images. Hematocrit was acquired on the
	same day in all subjects.
Number of Subjects	Enrollment:120[anticipate]
	PBC group: 60[anticipate]
	Healthy group:60[anticipate]
Enrollment Criteria	Inclusion criteria were:
	(1) All patients were PBC older than 18 without any cardiac symptoms.
	(2) The diagnosis of PBC was established when patients met at least two of three
	criteria:
	1) elevated alkaline phosphatase or γ -glutamine transpeptidase;
	2) positive anti-mitochondrial antibodies (AMA) or specific antinuclear antibody
	(ANA) (sp100, gp210) positive;
	3) histological findings of chronic and non-suppurative inflammation, which
	surrounds and destroys interlobular and septal bile ducts.
	Exclusion criteria were :
	(1) having cardiac discomfort or a prior history of heart disease, abnormal
	electrocardiographic results; stress echocardiography proved wall motion
	abnormality, coronary CT or angiography proved coronary artery stenosis >50% when
	Framingham risk score was over 10.
	(2) having cirrhosis or other known liver diseases such as viral hepatitis, alcohol-
	induced liver injury, drug-induced liver injury, and inherited metabolic liver disease.
	(3) life expectancy of less than 6 months due to any condition.
	(4) for magnetic resonance safety reasons: standard metallic contraindications to
	CMR, or severe infection and renal failure (i.e., an estimated glomerular filtration rate
	< 30 ml/min/1.73 m2);
	(5) patient with any medical conditions that in the opinion of the investigators will
	not be appropriate to participate in the study.
Safety Assessments	Participants will be assessed for AEs at scanning while on the study. Adverse events
	will be graded according to the CTCAE v4.03. Type, incidence, severity, timing,
	seriousness, and relatedness of AEs and laboratory abnormalities will be reported.
Endpoints	1.LGE and T2-STIR
	2.ECV mapping
Statistical Analysis	Continuous variables are expressed as median (quartile) and categorical variables
	as numbers and percentages. Ventricular volume was acquired by both
	echocardiography and CMR; the latter was used for analysis. For continuous
	variables, the Mann-Whitney U test was used to compare between two groups.

Categorical variables were compared using the Pearson's chi-squared test or Fisher's exact test. Logistic regression was used to identify the predictors of elevated ECV. Variables with P value <0.1 in univariable analyse were included into multivariable anaylse. Comparisons of variables between controls and PBC groups were adjusted for age and body surface area with covariance analysis. The interobserver reproducibility of CMR measurements was assessed using the interclass correlation coefficient (ICC), as well as intraclass coefficient analysis. The methods of sample size calculation could be found in supplementary materials. Statistical analysis was performed primarily using the SPSS 20.0 (SPSS Inc, Chicago, IL) system. P<.05 was statistically significant.

Sample Size Calculation. This study aimed to explore clinically silent myocardial impairments in PBC patients without presenting any reported cardiac clinical manifestation. According to previous CMR studies 3,4, ECV is one of the most valuable and sensitive indices reflecting myocardial change. In our pre-test including 10 PBC and 10 controls, the mean of ECV was 30% and 24%, respectively. The standard deviation of ECV in the entire group was 0.3. A margin of 4% was expected to differentiate between PBC and controls group. On the basis of margin and sample ratio (nPBC/nControl=1) and a type I error (two-side) of 5% and a power of 0.8, the final sample size required at least 42 subjects in each group.

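### PBC patients and controls need not be balanced within centre and centre is not in the analysis, so any between-site ECV offset would pass into the group difference

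*Combined protocol and SAP*

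**What the plan says.** All references are to the combined protocol and SAP.

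- **Study Design:** "EARLY-MYO-PBC study was a prospective, three-center, multi-modality cardiac imaging study". On image handling it says: "All images were acquired and then processed in a core lab 1". This can mean that scanning and reading both took place in one core lab, or that scans were acquired at the centres and only read centrally.
- **Study Design, image analysis:** "Hematocrit was acquired on the" same day as the scan in every subject. The laboratory is not named.
- **Number of Subjects:** the planned totals are "PBC group: 60[anticipate" and "Healthy group:60[anticipate". There are no numbers by centre, no matching and no stated source of controls.
- **Statistical Analysis:** for continuous "variables, the Mann-Whitney U test was used to compare between two groups", with chi-squared or Fisher tests for categorical data. The only adjustment of the group comparison is this: "Comparisons of variables between controls and PBC groups were adjusted for age and body surface area with covariance analysis". Centre is named in none of these analyses.

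**The concern.** Because group is not randomised, only the design or the model can keep a technical difference between sites out of the PBC-control contrast. Here neither is set up to do so. One centre could supply most patients and another most controls, and the plan would still have been followed. Age and body surface area do not carry a scanner or assay offset, so adjusting for them does not remove it. Central reading standardises interpretation, but does not by itself correct an offset already present in the T1 map or the haematocrit.

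At stake is ECV, the quantitative primary measure and the one on which the study is sized. The error could go either way: an offset could create or inflate a PBC effect, or hide one, depending on which group is concentrated at the higher-reading site.

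**Working it through.** **Inputs from the plan.** 60 per group; two-sided 5% test; power 0.80; margin 4 ECV points; pilot means 30% and 24%; at least 42 per group required.

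**Choice of SD.** The stated SD of 0.3 does not reproduce 42. With n = 2(1.96 + 0.84)²SD²/4², reading 0.3 as a fraction (30 points) gives 883 per group, and reading it as 0.3 points gives 1. Solving for n = 42 gives SD ≈ 6.5 points. That discrepancy is a separate matter. Here I use 6.5 (implied by 42) and 3 (a misplaced decimal) as a range.

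**Assumptions not in the plan.** Offsets across three centres of d, d/2 and 0 ECV points, with d = 1, 2 or 3; the centre shares below; no true PBC effect.

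**Bias.** Bias = Σ (PBC share − control share) × offset. For d = 3:

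- Moderate, PBC 50/25/25 v controls 25/25/50: 0.25 × 3 + 0 × 1.5 − 0.25 × 0 = 0.75 points.
- Intermediate, 50/30/20 v 20/30/50: 0.30 × 3 = 0.9 points.
- Strong, 70/20/10 v 10/20/70: 0.60 × 3 = 1.8 points.

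Against the 4-point margin these are 19%, 22.5% and 45%.

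**False-positive rate, checked by hand.** For the strong case at SD 6.5, the centre mix adds variance within each group of (0.7 × 9 + 0.2 × 2.25) − 2.4² = 0.99. Then SE = √[2(42.25 + 0.99)/60] = 1.20 and bias/SE = 1.50. The two-sided rejection rate is Φ(1.50 − 1.96) + Φ(−1.50 − 1.96) ≈ 32%. The same steps for the intermediate case give added variance 1.37, SE 1.21, bias/SE 0.75 and a rate of about 12%.

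**False-positive rate, simulated** (2,000 runs per cell, planned covariance analysis on age and body surface area):

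| Offset d | Imbalance | Bias (formula) | Rate, SD 3 | Rate, SD 6.5 |
|---|---|---|---|---|
| 1 | moderate | 0.25 | 7.6% | 5.1% |
| 2 | moderate | 0.50 | 15.4% | 7.2% |
| 3 | moderate | 0.75 | 25.2% | 10.2% |
| 1 | strong | 0.6 | 19.0% | 7.7% |
| 2 | strong | 1.2 | 56.0% | 16.2% |
| 3 | strong | 1.8 | 85.6% | 32.0% |

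Balanced centres give 5.0% to 5.9%. Mann-Whitney rates are nearly the same as those in the table.

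**With centre in the model.** Across all 18 scenarios (the six above and three balanced ones, some at each SD) the mean estimated difference lies between −0.06 and +0.03 points. Rejection is 3.9% to 6.6%, which is simulation scatter around 5%.

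**Price of adjustment.** Information on the group difference is Σ n₁n₂/(n₁ + n₂) over centres.

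- Balanced: 60 × 60/120 = 30.
- Strong imbalance: 42 × 6/48 + 12 × 12/24 + 6 × 42/48 = 5.25 + 6 + 5.25 = 16.5, equivalent to 33 balanced subjects per group.
- Power for 4 points at SD 6.5 falls from about 92% (60 per group) to about 70% (33 effective), below the planned 80%.
- Two-centre approximation, 42/(1 − δ²), where δ is the difference in centre share: 45, 56 and 96 per group for δ = 0.25, 0.50 and 0.75.

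**The case against.** A reader might infer that three centres contributed images. The documents do not establish this. The core-lab sentence, read literally, puts acquisition in one place, and then no scanner offset between centres can arise. The plan also fixes one T1 sequence and scheme, one contrast agent and dose, and one post-contrast time, and it refers to publications for further acquisition detail. This part of the objection stands, and it is why the point is conditional.

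On the single-site reading, haematocrit is the remaining technical route, and it is a weak one. Assuming ECV is proportional to (1 − haematocrit), with ECV near 27% (midpoint of 24% and 30%) and haematocrit between 0.38 and 0.45, a 3-point ECV offset needs a haematocrit shift of (3/27) × 0.62 to (3/27) × 0.55, about 6 to 7 points. Nothing says haematocrit was measured in different laboratories. The figures for 3-point offsets therefore belong to the multi-scanner reading.

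A reader might also infer that the 5% error rate is shown to be inflated. It is not. Offsets and shares are unknown, small offsets with moderate imbalance do little harm, and even a 1.8-point bias is under a third of the 6-point pilot difference.

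What the objection does not remove is the gap itself. Neither recruitment nor analysis accounts for centre in a three-centre, non-randomised comparison.

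**Conclusion.** The point holds conditionally. The text confirms that nothing requires balance within centre and that centre enters no planned group comparison. If images or haematocrit came from more than one site and centre shares differ between groups, the offset passes directly into the ECV difference.

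At SD 6.5, an assumed 3-point offset gives false-positive rates of about 10%, 12% and 32% for biases of 0.75, 0.9 and 1.8 points; the rates are higher if the SD is smaller. At 1 point with moderate imbalance the rate is 5% to 8%. If each group came from a different centre, the whole offset would become bias, so 2 points would be half the 4-point margin.

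These sizes rest on assumed offsets, shares and SDs. The plan should be improved on this point, but there is no evidence that the result is wrong.

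**What to change.** 1. State where images were acquired, on how many scanners, and where haematocrit was measured.
2. Recruit controls within each centre in proportion to its PBC patients and over the same calendar period.
3. Add centre as a fixed factor (2 degrees of freedom) to the covariance analysis of ECV, beside age and body surface area.
4. Stratify the LGE/T2-STIR comparison by centre, for example with a Mantel-Haenszel test.
5. Report the group-by-centre table.

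**Cost.** Control recruitment is slightly slower, and centre must be kept in the dataset; the documents do not list it among the data collected. The loss of precision is negligible when centres are balanced and large when they are not, as the working shows, so step 2 matters more than step 3.

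If enrolment is already complete and badly unbalanced, report the adjusted and unadjusted estimates together. If groups and centres are fully separated, no adjustment can rescue the comparison, and the report should say so.

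### The planned PBC–control comparison cannot separate an effect of PBC on ECV from comorbidity; recording three conditions and adding one restricted analysis would address this cheaply

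*Combined protocol and SAP*

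**What the plan says.** **Who may enter.** The inclusion criterion reads "All patients were PBC older than 18 without any cardiac symptoms", followed by the diagnostic definition. Under Enrollment Criteria, exclusion (1) removes patients "having cardiac discomfort or a prior history of heart disease, abnormal" electrocardiographic results. It also removes proven wall-motion abnormality and coronary stenosis above 50%, with a condition attached: "Framingham risk score was over 10". Exclusion (2) concerns the liver: "having cirrhosis or other known liver diseases such as viral hepatitis, alcohol"-induced injury and similar conditions. Exclusions (3) and (4) cover short life expectancy, MR safety, severe infection and renal failure. Exclusion (5) is discretionary: "patient with any medical conditions that in the opinion of the investigators will" make participation inappropriate.

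**The comparator.** The Number of Subjects row gives "Healthy group:60[anticipate"], against 60 PBC patients. No control criteria or matching are stated. Study Design adds that all participants had no cardiac discomfort, no history of heart disease and a normal ECG.

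**The analysis.** Under Statistical Analysis: "Comparisons of variables between controls and PBC groups were adjusted for age and body surface area with covariance analysis". Separately: "Logistic regression was used to identify the predictors of elevated ECV". The candidate predictors and the population for that model are not given.

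**The concern.** Primary Objectives describes ECV as a measure of change in the myocardial interstitial matrix. That is a description of tissue, not of cause. The hypothesis in Study Design is about cause: injury occurring early in PBC. The link between the two is the comparison with controls, and it carries the inference only if the groups are alike in other conditions that might move ECV.

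Nothing in the plan secures that. Hypertension, diabetes and a second autoimmune disease are not in themselves a history of heart disease, so a patient with any of them passes the listed criteria. The Framingham clause looks for coronary disease in higher-risk entrants, and a raised score alone excludes no one. If the control group is healthy in the ordinary sense, these conditions will be rarer there. Age and body surface area can stand in for comorbidity only in part, because two people of the same age and size can differ in it. What is at stake is whether an ECV difference can be described as related to PBC.

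**Working it through.** **1. Does any rule bar the three conditions?** Taking the five exclusions in turn: (1) cardiac symptoms, history, ECG and coronary or wall-motion findings; (2) liver disease; (3) life expectancy; (4) MR safety, infection and renal failure; (5) investigator opinion. None names hypertension, diabetes or another autoimmune disease. Only (5) could remove such patients, and it sets no common standard for the three centres.

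**2. Does the analysis balance them?** The stated covariates are age and body surface area. The logistic model could include comorbidity, but its candidates are unlisted, entry to the multivariable step depends on P < 0.1, and it is not the group contrast.

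**3. How large could the bias be?**

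bias = (comorbidity prevalence in PBC − prevalence in controls) × ECV shift per affected person

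The documents give none of these inputs, so all are assumed, including zero prevalence in controls. The within-group SD is also assumed. The stated SD of 0.3 has no clear unit, and read as 0.3 ECV points with a 4-point difference it would require only 1 per group (2 by t-test), not 42. Solving instead for the SD that gives 42 per group at a 4-point difference (two-sided 5%, power 0.80):

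SD = 4 / [(1.96 + 0.84) × √(2/42)] ≈ 6.5 points

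I use 4 and 6.5. The mismatch in the sample size calculation is a separate matter and does not bear on this point.

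The last two columns give simulated two-sided 5% rejection rates for a Mann–Whitney test with 60 per group, no true PBC effect and 4,000 runs:

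| Prevalence in PBC | Shift (points) | Bias (points) | Share of 4-point margin | Rejection, SD 4 | Rejection, SD about 6.5 |
|---|---|---|---|---|---|
| 10% | 1 | 0.1 | 2.5% | about 5% | about 5% |
| 30% | 2 | 0.6 | 15% | 12% | 7% |
| 40% | 3 | 1.2 | 30% | 34% | 17% |
| 50% | 4 | 2.0 | 50% | 69% | 37% |

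A repeat run agreed within about 2 percentage points. The simulated test is not adjusted for age or body surface area. Any part of the comorbidity effect that tracks those covariates would be reduced in the planned covariance analysis, so these rates do not describe that analysis.

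**4. Against the plan's own ECV figures.** The pilot difference is 30 − 24 = 6 points. The largest assumed bias is 2/4 = one half of the margin and 2/6 = one third of the pilot difference.

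**The case against.** The strongest reply is that the asymmetry is inferred from one word. The healthy label appears in a head-count row, while Statistical Analysis speaks only of controls. Study Design applies the same cardiac screen to all participants, and exclusion (1) is not expressly confined to PBC patients. Controls might carry the same conditions. This stands as far as it goes: the documents do not show that controls are free of comorbidity. Nor do they give any criterion or covariate that would make the groups alike.

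Second, exclusion (5) may remove some affected patients, and the Framingham clause shows that coronary risk was considered. Both are true. The first is discretionary. The second addresses coronary disease, not diffuse interstitial change, and says nothing about how many patients would exceed the threshold or why.

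Third, admitting PBC patients with common comorbidities is a legitimate choice of population for a study whose stated aim is to explore. I agree, and nothing here requires a change to eligibility.

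Fourth, a reader might infer that raised ECV could not be attributed to PBC at all. The documents do not support that. It would need a known imbalance and a known ECV effect large enough to account for the difference, and neither is given. Even the most adverse illustration stays below the margin. The 6-point pilot difference does not settle the matter in the other direction, because it comes from 10 versus 10 people whose comorbidities are not reported.

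**Conclusion.** The point holds as a cheap improvement to the plan. As written, the comparison cannot separate an effect of PBC on ECV from that of hypertension, diabetes or another autoimmune disease, and the estimated difference may be inflated by an unknown amount. Three features of the text support this: no listed exclusion bars these conditions, no criteria are stated for controls, and only two covariates are used, neither of which is comorbidity.

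The size is illustrative only. Over the assumed range it runs from negligible to 2 ECV points. Inflation or a spurious significant result is possible, but the material does not show that comorbidity would explain the whole of a 4-point or 6-point difference.

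**What to change.** - **Record** hypertension, diabetes and other autoimmune disease at enrolment, in both groups.
- **Prespecify a restricted analysis**: repeat the age- and body-surface-area-adjusted ECV comparison, and the LGE/T2-STIR comparison, with participants who have any of the three conditions removed from both groups.
- **Report** the restricted estimate and its confidence interval beside the main one, and describe a difference as PBC-related only with reference to both.
- **Where the groups overlap**, add the Framingham score as a covariate in a sensitivity analysis. Exclusion (1) already calls for the score; it would need to be available for controls too.

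The cost is three baseline fields, one repeated analysis and some precision. If prevalence in PBC is p and no control is affected, 60 × (1 − p) PBC patients remain: 54 at 10%, 42 at 30%, 36 at 40% and 30 at 50%. Above 30%, the restricted analysis therefore has fewer than the planned minimum of 42. With 30 versus 60 and equal SDs, the standard error grows by a factor of √[(1/30 + 1/60) / (2/60)] = √1.5 ≈ 1.22, so the confidence interval is about 22% wider. That is why the restricted result should be read as an estimate beside the main one and not as a second significance test.

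### The predictor analysis uses only a yes/no split of ECV, with no cut-off or analysis population stated; a continuous-ECV model in PBC patients should be added

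*Combined protocol and SAP*

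**What the plan says.** Under Primary Objectives, ECV is the quantitative measure: "Quantitative assessment in cardiac injury T1 mapping–derived extracellular volumes (ECV) were used to detect changes in the myocardium interstitial matrix". The Sample Size Calculation section says "ECV is one of the most valuable and sensitive indices reflecting myocardial change" and bases the study size on a difference in mean ECV. The group comparisons also keep measured values. Continuous variables are compared by the Mann-Whitney test, and "Comparisons of variables between controls and PBC groups were adjusted for age and body surface area with covariance analysis".

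The predictor analysis is different. The Statistical Analysis section says "Logistic regression was used to identify the predictors of elevated ECV". Variables reaching P<0.1 one at a time go into a multivariable model, and significance is at P<.05. No section gives a cut-off, reference range or percentile for elevated, or lists the candidates.

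The Number of Subjects row gives "Enrollment:120[anticipate" and "PBC group: 60[anticipate", but nothing says which of these sets enters the model. In the pre-test (10 PBC, 10 controls), "the mean of ECV was 30% and 24%, respectively". The predictor analysis is not a listed objective or endpoint and has no power statement.

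**The concern.** Two separate things are at stake.

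1. **Information.** If a covariate shifts ECV by degrees, reducing ECV to elevated or not throws away part of what was measured. With 60 PBC patients, a real correlate is then easier to miss than it needs to be. Because the cut-off is not fixed, it could also be chosen after the data are seen.

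2. **Population.** The pre-test means differ by 6 ECV points between the groups. In a pooled model without a group term, disease status itself drives elevated ECV. A variable that only distinguishes PBC patients from controls could then be reported as a predictor of ECV.

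**Working it through.** **The plan's own figure.** There is none for this analysis. The only computed figure is for the group comparison: "the final sample size required at least 42 subjects in each group". With n = 2(1.96+0.84)²SD²/4², 42 per group corresponds to an SD of 4×√21/2.80 = 6.5 points. The stated SD of 0.3 does not reproduce it: read as a fraction (30 points) it gives 883 per group, and read as 0.3 points it gives 1. The point here does not depend on that figure; 6.5 is used below only as one plausible within-group SD.

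**Inputs.** From the documents: 60 PBC patients, 60 controls, pre-test means 30% and 24%, the P<0.1 screen, and two-sided 0.05. Assumed: one normal covariate, correlation r with ECV, and 50, 30 or 20% of patients elevated (50-80% mirrors 20-50%).

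**Step 1: information kept by the split.** The fraction is φ(z)²/(p(1−p)), where z is the cut-off that leaves a proportion p elevated. It is 0.637, 0.576 and 0.490 at p = 0.5, 0.3 and 0.2, so 36, 42 and 51% is discarded.

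**Step 2: approximate power, n = 60, r = 0.35.** Power ≈ Φ(atanh(r)√(n−3) − 1.96).
- Continuous: 0.3654×7.550 − 1.96 = 0.80, power 79%.
- Split, with r multiplied by the square root of the fraction in step 1, giving r = 0.279, 0.266 and 0.245: power 58, 54 and 47%.

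**Step 3: simulation, n = 60, r = 0.35 (40,000 runs).**

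| Elevated | Linear | Logistic, Wald | Logistic, likelihood-ratio |
|---|---|---|---|
| 50% | 80% | 57% | 61% |
| 30% | 80% | 52% | 57% |
| 20% | 80% | 45% | 49% |

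The loss runs from 79.9 − 61.4 = 18 points to 79.9 − 44.5 = 35 points.

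**Step 4: other correlations, n = 60, same proportions and both tests.** The loss is 10-17 points at r = 0.20, 14-26 at 0.25, 18-32 at 0.30, 12-28 at 0.45 and about 7-22 at 0.50.

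**Step 5: the plan's two-step procedure.** With five candidates, one real at r = 0.35, and the P<0.1 screen kept in both models (3,000 runs), power is 77% linear against 56/50/41% logistic. The chance of any false predictor among the other four is 16% against 16/16/14%. With all five null it is 23% against 20/18/19%.

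**Step 6: skewed ECV.** With lognormal ECV (log-SD 0.3 and 0.5, r = 0.35 on the log scale) and robust standard errors, linear power is 76% and 73%, against about 57/52/45% for the logistic Wald test.

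**Step 7: present-or-absent involvement.** Here the covariate acts on whether a patient is involved (latent correlation 0.35-0.55), with 50% or 30% involved. Uninvolved patients have mean 24 and the overall PBC mean is 30, so involved patients have mean 24 + 6/0.5 = 36 or 24 + 6/0.3 = 44. SD is 2-4 points, and elevated means above the controls' 95th centile. Over 10,000 runs per setting, logistic ranges from about 8 points worse to 6 points better than linear. With 50% involved, SD 3 and latent correlation 0.45: linear 73%, logistic 76% (Wald) or 79% (likelihood-ratio). With 30% involved, SD 2 and latent correlation 0.45: linear 76%, logistic 68% or 72%.

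**Step 8: pooling 60 + 60 without a group term.** Take a covariate unrelated to ECV within either group but 1 SD apart between them. The induced correlation is (3×0.5)/√(1.25×(SD²+9)), which is 0.316 at SD 3 and 0.187 at SD 6.5. The formula in step 2 with n = 120 then gives 94% and 54% for linear regression. By simulation, at SD 3/4/5/6.5, the covariate is flagged in 96/86/73/54% of runs by linear regression and 88/60/40/24% by logistic.

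**The case against.** The strongest objection is that the power loss follows from the assumed model. A smooth, monotone relation guarantees that splitting loses information, whereas the plan partly treats injury as present or absent: its first objective is the incidence of involvement. Step 7 bears this out, so the loss is conditional on a graded relation.

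The headline setting is also unfavourable to the plan. A correlation of 0.35 is about where linear power reaches 80% with 60 patients, close to where the loss is largest, and the 35-point end needs 20% elevated and a Wald test. If elevated meant above the controls' 95th centile, the pre-test means would put Φ(6/SD − 1.645) = 64/44/33/24% of PBC patients above it at SD 3/4/5/6.5, so 20% lies just outside that range. This stands as a caution on the upper end.

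A third objection is that asking who has abnormal ECV is a legitimate question in its own right. It is, and so the logistic model should stay. That does not supply the missing cut-off or population, or explain why the continuous values go unused.

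A reader might carry the graded calculation over to all 120 participants, which would give a loss of 9-21 points at r = 0.35. The documents do not support that figure: it treats two groups with pre-test means of 30% and 24% as one population. A reader might also take the pooling problem as an argument for linear regression. It is not, because linear regression flags the spurious covariate more often (step 8). It argues for restricting the population.

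**Conclusion.** The concern holds in a conditional form. The only planned predictor analysis rests on an undefined binary outcome in an unstated population. If covariates act on ECV in a graded way, then with 60 PBC patients, r = 0.35 and 20-50% elevated, the split costs 18-35 points of power (about 80% down to 45-61%); at r = 0.50 it costs about 7-22. The correlation, the proportion elevated and the graded relation are not in the documents. If covariates act on present-or-absent involvement, neither model has a consistent advantage.

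The pooling risk is separate and applies to both models. Its size depends on the assumed within-group SD and on a covariate gap of 1 SD.

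A reader might infer that the plan generally loses a third of its power, that logistic regression is an error, or that the main results are weakened. The documents support none of these. Only an exploratory analysis is affected; the group comparisons of ECV and the listed endpoints are not. The change is worth making because it is cheap and uses data already collected.

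**What to change.** Replace the logistic-regression sentence in the Statistical Analysis section with wording to this effect:

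*The predictor analysis is restricted to PBC patients. Continuous ECV is analysed by linear regression on a short list of covariates (about five) named in advance; coefficients are reported in ECV points with 95% confidence intervals, using robust standard errors if residuals are skewed. Logistic regression on elevated ECV is reported alongside, with its cut-off fixed in advance. Both analyses are exploratory.*

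The P<0.1 screening step may stay.

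**Cost.** SAP wording and a small amount of code, with no new data. There will be two sets of exploratory results, one in ECV points and one in odds ratios, and they may not agree. The false-predictor rate is not reduced: with five null candidates it is about 23% for the linear model against 18-20% for the planned one. That is why the exploratory label is needed.
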